7.3 Liver safety monitoring

To ensure patient safety and enhance reliability in determining the hepatotoxic potential of an investigational drug, a standardized process for identification, monitoring and evaluation of liver events has to be followed.

Liver events are divided into two categories:

- Liver events of special interest, which consist of liver function test (LFT) elevations.
- Medically significant liver events that are considered as serious adverse events and consist of marked elevations of LFTs and / or pre-specified adverse events.

Please refer to [Table 14-1](#) in [Appendix 2](#) for complete definitions of liver events.

Any liver event that meets the criteria for “**medically significant**” event, as outlined in [Table 14-1](#) of [Appendix 2](#), should follow the **standard procedures for SAE reporting** as described in [Section 7.2](#).

Every liver event as defined in [Table 14-1](#) of [Appendix 2](#) should be followed up by the investigator or designated personal at the trial site as summarized below.

- Repeat the LFT to confirm elevation as appropriate.
- Discontinue the investigational drug if appropriate.
- Hospitalize the patient if appropriate.
- Assess the causality of the liver event via exclusion of alternative causes (e.g., disease, co-mediations).
- An investigation of the liver event needs to be followed until resolution.

These investigations can include serology tests, imaging and pathology assessments, hepatology consultancy, based on the investigator's discretion. All follow-up information and the procedures performed should be recorded on appropriate CRF pages, including the liver event overview CRF pages.

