Normal blood pressure will be defined as a systolic pressure of 90 to <120 mmHg, and a diastolic blood pressure of 60 to <80 mmHg. Notable blood pressure will be hypertension (systolic blood pressure of ≥ 140 mmHg and/or diastolic blood pressure of ≥ 90 mmHg) or hypotension (systolic blood pressure of <90 mmHg and/or a diastolic blood pressure of <60 mmHg). A blood pressure indicative of prehypertension (systolic blood pressure of 120 to

<140 mmHg and/or diastolic blood pressure of 80 to <90 mmHg) will not be regarded as notable.

A normal pulse rate will be defined as a rate of 60 to 100 beats per minute (bpm). Notable pulse rates are a rate below 60 bpm (bradycardia) or above 100 bpm (tachycardia). Whether action needs to be taken to address notable vital signs will be decided by the investigator, taking into account the overall status of the patient. No specific action is foreseen as part of the study protocol.

14 Appendix 2: Liver event definitions and follow-up requirements

Table 14-1: Liver Event Definitions

	Definition/ threshold
Adverse event of special interest	
Laboratory values	ALT or AST > 3 x ULN ALP > 2 x ULN TBL > 1.5 x ULN
Medically significant event (SAE)	
Laboratory values	ALT or AST > 5 x ULN (with or without TBL > 2 x ULN [mainly conjugated fraction]) ALP > 5 x ULN (with or without TBL > 2 x ULN [mainly conjugated fraction]) TBL > 3 x ULN Potential Hy's Law cases (defined as ALT/AST > 3 x ULN and TBL > 2 x ULN [mainly conjugated fraction] without notable increase in ALP to > 2 x ULN)
Adverse events	Any clinical event of jaundice (or equivalent term) ALT or AST > 3 x ULN accompanied by general malaise, fatigue, abdominal pain, nausea, or vomiting, or rash with eosinophilia Any event that links to a preferred term (PT) in the MedDRA dictionary falling under the SMQ sub-module "Drug-related hepatic disorders – severe events only"* or any "Hy's law case" PT

* These events cover the following: hepatic failure, fibrosis and cirrhosis, and other liver damage-related conditions; non-infectious hepatitis; benign, malignant and unspecified liver neoplasms

Table 14-2: Liver Event Follow Up Requirements

Criteria	Event type	Actions required	Follow-up monitoring
Potential Hy's Law case ^a	Medically significant	Discontinue the study drug immediately Hospitalize, if clinically appropriate Report to Novartis as an SAE Establish causality	ALT, AST, TBL, Alb, PT, ALP and γ GT until resolution ^c (frequency at investigator discretion)

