ALT or AST			
> 8 x ULN	Medically significant	Repeat LFT within 48 hours If elevation persists, discontinue the study drug immediately Hospitalize if clinically appropriate Report to Novartis as an SAE Establish causality	ALT, AST, TBL, Alb, PT, ALP and γ GT until resolution ^c (frequency at investigator discretion)
> 5 to \leq 8 x ULN	Medically significant	Repeat LFT within 48 hours If elevation persists for more than 2 weeks , discontinue the study drug Report to Novartis as an SAE Establish causality	ALT, AST, TBL, Alb, PT, ALP and γ GT until resolution ^c (frequency at investigator discretion)
> 3 x ULN accompanied by symptoms ^b	Medically significant	Discontinue the study drug immediately Hospitalize if clinically appropriate Report to Novartis as an SAE Establish causality	ALT, AST, TBL, Alb, PT, ALP and γ GT until resolution ^c (frequency at investigator discretion)
> 3 to \leq 5 x ULN (patient is asymptomatic)	AESI	Central laboratory to report to Investigator & Novartis Repeat LFT once or twice in the week If elevation persists, establish causality	Investigator discretion Monitor LFT within 1 to 4 weeks or at next visit
\leq 3 x ULN (patient is asymptomatic)	N/A	Repeat LFT at next visit	
ALP (isolated)			
> 5 x ULN	Medically significant	Repeat LFT within 48 hours If elevation persists, report to Novartis as an SAE Establish causality	Investigator discretion Monitor LFT within 1 to 4 weeks or at next visit
> 2 to \leq 5 x ULN (patient is asymptomatic)	AESI	Central laboratory to report to Investigator & Novartis Repeat LFT once or twice in the week If elevation persists, establish causality	Investigator discretion Monitor LFT within 1 to 4 weeks or at next visit
\leq 2 x ULN (patient is asymptomatic)	N/A	Repeat LFT at next visit	

Criteria	Event type	Actions required	Follow-up monitoring
asymptomatic)			
TBL (isolated)			
> 3 x ULN	Medically significant	Repeat LFT within 48 hours If elevation persists, discontinue the study drug immediately Hospitalize if clinically appropriate Report to Novartis as an SAE Establish causality	ALT, AST, TBL, Alb, PT, ALP and γ GT until resolution ^c (frequency at investigator discretion) Test for hemolysis (e.g., reticulocytes, haptoglobin, unconjugated [indirect] bilirubin)

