2.1.1.7 Multiple assessments within visit windows

When there are *multiple assessments* in a particular visit window, the following rules are applied to select one value "representing" the subject in summary statistics in a visit window (SeeTable 2-2).

Novartis	For business use only	Page 16
SAP Amendment 2.0		AIN457AIT01

For baseline assessment definition see in Section 2.1.1.4. For post-baseline visit windows the following applies (unless otherwise specified):

- for *quantitative variables*, the *closest* to the actual visit is chosen (if two assessments have the same distance, then the earlier one will be chosen)
- for *qualitative variables*, the *worst* record is selected. It is noted that in the analyses performed, *worst* case is always well defined (e.g., for urine protein values "+" and "++", the worst case is defined as "++")

in case qualitative variables are based on quantitative variables, e.g. PASI 75 response, the visit will be assigned to the quantitative variable, and this visit will be used for the derived qualitative variable.

Timing of measurement	Type of data	Rule
Baseline	All data	See section 2.1.1.4
Post-baseline efficacy	All data except DLQI, HADS	The measurement closest to the target day will be used. In the event two measurements are taken equally apart (e.g., 1 day before target date and 1 day after), the earlier one will be used.
Post-baseline efficacy	DLQI,HADS	The measurement closest to the target day will be used. In the event two measurements are taken equally apart, the earlier one will be used. If two measurements have been taken on the same day, select the worst.
Post-baseline safety	Summary visit information (e.g. laboratory values, vital signs etc.)	The (non-missing) measurement closest to the target day will be used. In the event two measurements are taken equally apart (e.g., 1 day before target date and 1 day after), the earlier one will be used. If two measurments are taken on the same day then select the first one (using the time). If two measurements are taken on the same date/time then use the first visit number (assuming this is the planned visit).

Table 2-2 Rules for selecting values for analysis

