2.8 Safety analyses

All the safety analysis will be performed on Safety set by study phase (i.e. CORE and Extensions) and overall.

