2.8.3 Laboratory data

Summary statistics of laboratory data and absolute and changes from baseline will be provided by visit and cohort. Summaries will be provided on the following laboratory test and their parameters;

Hematology: Hemoglobin, hematocrit, red blood cell count, white blood cell count with differential (e.g. neutrophils, basophils, eosinophils, monocytes, lymphocytes) and platelet count.

Chemistry: Albumin, alkaline phosphatase, total bilirubin, bicarbonate/CO2, calcium, cholesterol, chloride, creatinine, CK, GGT, glucose, LDH, inorganic phosphorus, lipase, amylase, magnesium, potassium, total protein, AST, ALT, sodium, triglycerides, urea/BUN and uric acid.

Urinalysis: Specific gravity, pH. Summary table of change from baseline will not be perfomed for specific gravity, since the data captured by sites are in different ranges, which cannot be converted.

hsCRP

Patients with values above (H) or below (L) notable criteria (Table 2.8.3) will be listed and absolute and relative frequencies will be presented by visit and cohort. Laboratory values will be presented for each patient in a data listing with an indication of whether the value is above (H) or below (L) the normal reference range.

Laboratory data will also be summarized by presenting shift tables for each laboratory parameter showing the number and percentage of patients in each cohort with the most extreme post-baseline value that falls outside normal ranges by the classification of value at baseline (H/N/L).

For urinalysis of categorical variables (Glucose, Protein, Blood, WBC, RBC), summary table of number and percentage of patients by cohort and visit will be presented.

Laboratory parameter	Criterion for notable abnormalities
Liver Function and Relat	ted Variables
ALT (SGPT)	> 3 x Upper Limit of Normal (ULN)
AST (SGOT)	> 3 x ULN
Total bilirubin	> 2 x ULN

Table 2.8.3 Clinically notable laboratory abnormalities

Alkaline phosphatase (ALP)	> 2.5 x ULN
Renal Function and Elec	trolyte Variables
Serum Creatinine	> 1.5 x ULN
Potassium	> 6 mmol/L or < 3 mmol/L
Sodium	> 160 mmol/L or < 115 mmol/L
Hematology Variables	
Hemoglobin	\geq 20 g/dL decrease from baseline
Platelet count	< Lower Limit of Normal (LLN)
White blood cell count	< 0.8 x LLN
Neutrophils	< 0.9 x LLN
Eosinophils	> 1.1 x ULN
Lymphocytes	> 1.1 x ULN
Urinalysis Variable	
Protein urine dipstick	++* (*++ is > 100 mg/dL)

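### Notable laboratory values and vital signs are counted only by visit, so no by-cohort count of patients who ever crossed a limit is produced, and the protocol's first-tier liver events have no SAP summary

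*SAP*

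**What the plan says.** **Notable values.** SAP 2.8.3 states that patients beyond the limits of Table 2.8.3 "will be listed and absolute and relative frequencies will be presented by visit and cohort". SAP 2.8.4.3 plans the same output for blood pressure and pulse. Protocol 9.5.2 asks for this layout with the limits of Protocol Appendix 1.

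**Periods.** SAP 2.8 opens with a general rule: "All the safety analysis will be performed on Safety set by study phase (i.e. CORE and Extensions) and overall".

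**Which value enters a visit.** For post-baseline safety data, SAP Table 2-2 says: "The (non-missing) measurement closest to the target day will be used". Ties go to the earlier value. For a category derived from a number, SAP 2.1.1.7 assigns the visit to the number first, and "this visit will be used for the derived qualitative variable".

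**Worst-value output.** SAP 2.8.3 adds a laboratory shift table of the most extreme post-baseline value, graded high, normal or low against the reference range. SAP 2.8.4.3 has no equivalent.

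**Liver events.** Protocol 7.3 defines two tiers. The first is "Liver events of special interest, which consist of liver function test (LFT) elevations", with limits in Protocol Appendix 2, Table 14-1: "ALT or AST > 3 x ULN ALP > 2 x ULN TBL > 1.5 x ULN". The second is medically significant events, which follow SAE reporting. For first-tier elevations Table 14-2 instructs: "Repeat LFT once or twice in the week". Follow-up results "should be recorded on appropriate CRF pages, including the liver event overview CRF pages". SAP 2.8.1.1 names neutropenia and candida infection as the adverse events of special interest. Its risk-management table covers infections, neutropenia, tumours, MACE, immunogenicity, Crohn's disease and hepatitis B reactivation, with no row for liver tests.

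**The concern.** Comparing safety and tolerability between the Cw6 cohorts is a stated secondary objective. The usual question is how many patients in each cohort ever crossed a notable limit on treatment. By-visit frequencies do not answer it, because the same patient may appear at several visits or different patients at each. The selection rule adds a second problem: it favours closeness to the target day over severity, so a notable value can be in the database and absent from the frequency table.

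The protocol also sets up collection of liver events as a distinct category, with its own thresholds and CRF pages, but the SAP plans no table for the first tier. As written, a reader who wants these rates by cohort has to count them from listings.

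**Working it through.** The documents give no figure to reproduce. The check compares the texts, with simple arithmetic on the selection rule.

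**1. Can a patient-level rate be recovered from by-visit frequencies?** Laboratory tests and vital signs are scheduled after baseline at visits 7 to 12 (6 visits) and E1 to E4 (4 visits), 10 in all (Protocol Tables 6-1 and 6-2). If a share p of the same patients is notable at each of n visits, the share ever notable lies between p (the same patients every time) and n × p (different patients every time). That is 1 to 6 times p over the core visits, and 1 to 10 times p for patients who attend all ten. The documents give no p, so this shows only that the rate cannot be recovered; it is not an estimate.

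**2. Can a notable value drop out?** The week 16 window is Day 99 to 126, with target Day 112 (SAP Table 2.1).

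- Off-target sample: a normal scheduled value on Day 112 is 0 days from target, and a notable unscheduled value on Day 120 is 8 days from it. The normal value is kept.
- Liver repeat: ALT at 4 × ULN on Day 105 is 7 days from target, and 2 × ULN on Day 110 is 2 days from it. The repeat is kept and the patient is tabulated as not notable.

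In general, let the first sample be x days from target (negative if early) and the repeat g days later. The repeat replaces it when |x + g| < |x|, that is, when x < −g/2. So the visit must be early by more than half the gap. A visit on or after target is never displaced by a later repeat. The liver example also requires repeats to be stored with the scheduled samples, which the documents do not settle. For vital signs the protocol requires no repeat, so only unscheduled readings matter.

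**3. Does the shift table fill the gap?** For platelets it does, because the notable limit is the lower limit of normal. For neutrophils (0.9 × LLN), eosinophils and lymphocytes (1.1 × ULN) it nearly does. For ALT and AST (3 × ULN), bilirubin (2 × ULN), ALP (2.5 × ULN) and creatinine (1.5 × ULN) it does not: everything above ULN falls in one class.

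**4. Liver limits side by side (multiples of ULN).**

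| Test | Protocol Table 14-1, first tier | Protocol Appendix 1 | SAP Table 2.8.3 | First-tier event but not notable |
|---|---|---|---|---|
| ALT, AST | > 3 | > 3 | > 3 | none |
| ALP | > 2 | > 2.5 | > 2.5 | > 2 to 2.5 |
| Total bilirubin | > 1.5 | > 2 | > 2 | > 1.5 to 2 |

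Exclusion criterion 16 removes patients with ALP above 2 or bilirubin above 1.5 × ULN at screening (Gilbert syndrome excepted), so crossing these limits on treatment would mostly be new.

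**5. Do the adverse event tables cover it?** In part. ALT or AST above 5, bilirubin above 3 × ULN, potential Hy's Law cases and the other medically significant events go through SAE reporting; for isolated ALP above 5 × ULN, Table 14-2 makes this depend on persistence. The SAE tables by cohort therefore include them, without the threshold. Under Protocol 7.1 a lower, asymptomatic elevation counts as an adverse event only if judged clinically significant or in need of therapy.

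**6. Follow-up.** About 306 of 406 patients are planned to enter the extension, so 406 − 306 = 100 (100/406 = 24.6%) are not. Entry requires a PASI 75 response (Protocol 4.3). Ever-crossed rates therefore need exposure time beside them.

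**The case against.** The SAP does what the protocol's analysis section asks. Its ALP and bilirubin limits are those of Appendix 1, and Protocol 9.5.2 prescribes the by-visit layout. A reader might infer that the SAP altered or contradicted the protocol's limits. It did not. Appendix 2 sets separate site reporting and follow-up triggers, and 9.5.2 does not name them as analysis criteria. What remains is that a category the protocol defines and collects has no planned summary.

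A reader might also infer that serious liver signals would go unseen. The documents do not support that either. Medically significant events are reported as SAEs, every notable value is listed, and the shift table uses the most extreme value. The gap concerns the first tier and the missing patient count.

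The rule in SAP 2.8 on phase and overall could be read as implying an overall count. It fixes the periods, but not what makes a patient notable over a period or which samples count, and the specific text for notable values says by visit.

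Finally, displacement by a repeat is conditional. It needs an early visit, a short gap, a repeat at or below the limit, and storage with the scheduled samples. That objection stands against any percentage for lost values. It does not touch the missing patient count or the missing liver summary, which follow from the text alone.

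**Conclusion.** The point holds as a minor gap in the safety analysis. The plan yields no by-cohort count of patients who ever crossed a notable limit. Its by-visit tables can omit a notable value when another sample in the window is closer to target. First-tier liver events have no dedicated summary.

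The size cannot be stated: no event rates are given, and where repeats are stored is not specified. The selection rule is the same in both cohorts, so this is incomplete counting; a reader who inferred a bias between cohorts would go beyond the documents. The primary PASI 90 result is unaffected. SAP sections 2.12 and 2.13 are not visible in the public text, and nothing is inferred from them.

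**What to change.** In SAP 2.8.3 and 2.8.4.3, add the number and percentage of patients with at least one newly occurring notable post-baseline value, by cohort, for core, extension and overall. Use all scheduled, unscheduled and repeat samples, with patients who did not meet the criterion at baseline as the denominator. State that the closest-to-target rule of Table 2-2 does not apply to these counts, and name the CRF pages that supply repeat tests.

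Add the same count for the first-tier thresholds of Protocol Table 14-1 (ALT or AST above 3, ALP above 2, bilirubin above 1.5 × ULN). Show exposure time beside the rates.

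Correct the haemoglobin limit before including it. A decrease of at least 20 g/dL would need a baseline of at least 20 g/dL, so the criterion cannot in practice be met.

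The cost is SAP wording and one extra table per domain from data already collected. Reported rates will be higher, and isolated readings such as a single pulse below 60 will count. Patients who are tested more often have more chances to be counted. Results held on the liver-event CRF pages may have to be merged with the laboratory data.

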2.8.4 Other safety data

2.8.4.1 ECG and cardiac imaging data

Summary of normal and abnormal ECG findings at screening will be presented by cohort on Safety set.

Listing will be provided for the normal and abnormal ECG findings at screening on Safety set.

2.8.4.2 Chest X-ray

Summary of normal and abnormal Chest X-ray findings at screening will be presented by cohort on Safety set.

Listing will be provided for the normal and abnormal Chest X-ray findings at screening on Safety set.

2.8.4.3 Vital signs

Vital signs data (sitting pulse rate, sitting systolic and diastolic blood pressure) will be summarized on Safety set.

Summary statistics of vital signs and changes from baseline will be provided by visit and cohort. Clinically notable vital signs (Table 2.8.4.3) will be listed and absolute and relative frequencies will be presented by visit and cohort.

Vital sign (unit) parameter	Notable abnormalities
Systolic blood pressure (mmHg)	>= 140 mmHg or < 90 mmHg
Diastolic blood pressure (mmHg)	>=90 mmHg or <60 mmHg
Pulse (bpm)	> 100 bpm or <60 bpm

 Table 2.8.4.3
 Criteria for notable vital sign abnormalities

2.8.4.4 Height, weight and waist

Summary statistics n, mean, median, standard deviation, first and third quartiles, minimum and maximum will be provided for weight, waist circumference and derived BMI (calculated from body weight and height) by visit and cohort including changes from baseline.

An ANCOVA model will be fitted, adjusting by sex and age, in order to evaluate differences between cohorts in weight, waist and BMI changes vs baseline at each time point.

2.9 Pharmacokinetic endpoints

Not applicable.

2.10 PD and PK/PD analyses

Not applicable.

2.11 Patient-reported outcomes

Variables related to health-related quality of life (HR-QoL) are described below. All HR-QoL variables will be evaluated based on Safety set. Both prevalence and LOCF approach will be adopted.

Dermatology Life Quality Index

Seven scores will be derived from the DLQI: the total score of each of the six dimensions as well as the total score over all items. The higher the score, the more quality of life is impaired.

The percentage change from baseline will be derived for each of the seven scores. Summary statistics will be provided for absolute values as well as for the percentage change by visit.

Changes from baseline in DLQI at each time point will be analyzed by means of a paired ttest or Wilcoxon signed-rank test, based on data distribution.

In addition, summary statistics will be provided for the number of patients achieving DLQI 0 or 1 at each time point specifying absolute and relative frequency of patients with DLQI 0/1 response. Further, comparison between baseline and each time point for proportion of patients achieving DLQI 0 or 1 will be performed using McNemar's test.

Following details to the DLQI scoring: The scoring of each question is as follows

- Very much: scored 3
- A lot: scored 2
- A little: scored 1

- Not at all: scored 0
- Not relevant: scored 0
- Question unanswered: scored 0
- Question 7: "prevented work or studying": scored 3

The DLQI total score will be calculated by summing the score of each question resulting in a maximum of 30 and a minimum of 0. The highger the score, the more quality of life is impaired.

Meaning of DLQI scores:

- 0-1= no effect at all on patient's life
- 2-5= small effect on patient's life
- 6-10= moderate effect on patient's life
- 11-20= very large effect on patient's life
- 21-30= extremely large effect on patient's life

The DLQI will be analyzed under six headings as follows:

- Symptoms and feelings: questions 1 and 2, score maximum 6
- Daily activities: questions 3 and 4, score maximum 6
- Leisure: questions 5 and 6, score maximum 6
- Work and school: question 7, score maximum 3
- Personal relationships: question 8 and 9, score maximum 6
- Treatment: question 10, score maximum 3

Interpretation of incorrectly completed questinnaires:

There is very high success rate of accurate completion of the DLQI. However, sometimes patients do make mistakes.

- 1. If one question is left unanswered this is scored as 0.
- 2. If two or more questions are left unanswered the questionnaire will not be scored.
- 3. If question 7 is answered 'yes' this will be scored 3. If question 7 will be answered 'no' or 'not relevant' but then either 'a lot' or 'a little' is ticked this will then be scored 2 or 1.
- 4. If two or more response options are ticked, the response option with the highest score will be recorded.
- 5. If there is a response between two tick boxes, the lower of the two csore options will be recored.
- 6. If one item is missing from a two-item subscale that subscale will note be scored.

Hospital Anxiety and Depression Scale

Descriptive statistics of HAD-A and HAD-D score at each time point with change from baseline will be provided. Changes from baseline to each time point will be analyzed by means of a paired t-test or Wilcoxon signed-rank test, based on data distribution.

The sub-scores HAD-A and HAD-D, will be displayed per class (i.e. scores ≥ 11 indicate the presence of anxious or depressive disorders; scores between 8-10 points are borderline abnormal, and scores of ≤ 7 indicate that the disorder is not present) at each time point by means of a shift table.

In addition, the prevalence of anxiety and depression will be presented on the basis of the following three criteria:

following three criteria:

- As per the score on the corresponding sub-scores of the HAD Questionnaire
- In terms of the treatment they are receiving for anxiety/depression.
- According to both criteria.

Following details to the HADS scoring: The scoring of each question is as follows:

I feel tense or 'wound up':	Α	I feel as if I am slowed down:	D
Most of the time	3	Nearly all of the time	3
A lot of the time	2	Very often	2
Time to time, occasionally	1	Sometimes	1
Not at all	0	Not at all	0
I still enjoy the things I used to enjoy:	D	I get a sort of frightened feeling like 'butterflies in the stomach':	Α
Definitely as much	0	Not at all	0
Not quite so much	1	Occasionally	1
Only a little	2	Quite often	2
Not at all	3	Very often	3
I get a sort of frightened feeling like something awful is about to happen:	А	I have lost interest in my appearance:	D
Very definitely and quite badly	3	Definitely	3
Yes, but not too badly	2	I don't take as much care as I should	2
A little, but it doesn't worry me	1	I may not take quite as much care	1
Not at all	0	I take just as much care as ever	0
I can laugh and see the funny side of things:	D	I feel restless as if I have to be on the move:	A
